5.4.20 Prevention and Treatment of Hemorrhagic Events

Management of cabozantinib associated hemorrhagic events:

Hemorrhagic events have been reported with approved drugs that inhibit VEGF pathways as well as with cabozantinib. As preventive measures, subjects should be evaluated for potential bleeding risk factors prior to initiating cabozantinib treatment and monitored for bleeding events with serial complete blood counts and physical examination while on study.

Risk factors for hemorrhagic events may include (but may not be limited to) the following:

- Tumor lesions with cavitations or tumor lesions which invade, encase, or abut major blood vessels.
- Recent or concurrent radiation to the thoracic cavity.
- Active peptic ulcer disease, ulcerative colitis, and other inflammatory GI diseases.
- Underlying medical conditions which affect normal hemostasis (e.g., deficiencies in clotting factors and/or platelet function, or thrombocytopenia).
- Concomitant medication with anticoagulants or other drugs which affect normal hemostasis.
- History of clinically significant hemoptysis.

Management: Cabozantinib should be discontinued in subjects with serious (Grade 3) and life-threatening (Grade 4) bleeding events or recent hemoptysis (≥ 0.5 teaspoon (2.5mL) of red blood). Treatment with cabozantinib should be held if less severe forms of clinically significant hemorrhage occur and may be restarted after the cause of hemorrhage has been identified and the risk of bleeding has subsided at a dose agreed to by the Study Chair and the investigator. Therapy

of bleeding events should include supportive care and standard medical interventions.

Furthermore, subjects who develop tumors abutting, encasing, or invading a major blood vessel or who develop cavitation of their pulmonary tumors while on study treatment should be considered for discontinuation of cabozantinib treatment.

5.4.21 Rectal and Perirectal Abscess and GI and non-GI Perforation/Fistula Formation/

Management of cabozantinib-associated rectal and perirectal abscess: Rectal and perirectal abscesses have been reported, often in subjects with concurrent diarrhea.

These should be treated with appropriate local care and antibiotic therapy. Cabozantinib should be held until adequate healing has taken place.

Management of cabozantinib associated GI Perforation/Fistula:

GI perforation/fistula and Non-GI fistula formation have been reported with approved drugs that inhibit VEGF pathways as well as with cabozantinib. Carefully monitor for episodes of abdominal pain, especially in subjects with known risk factors for developing GI perforation/fistula or non-GI fistula, to allow for early diagnosis.

Risk factors include the following:

- Intra-abdominal tumor/metastases invading GI mucosa.
- Active peptic ulcer disease, inflammatory bowel disease, ulcerative colitis, diverticulitis, cholecystitis or symptomatic cholangitis, or appendicitis
- History of abdominal fistula, GI perforation, bowel obstruction, or intra-abdominal abscess
- Prior GI surgery (particularly when associated with delayed or incomplete healing). Complete healing following abdominal surgery or resolution of intra abdominal abscess must be confirmed prior to initiating treatment with cabozantinib.
- Radiation to the GI tract

Additional risk factors include concurrent chronic use of steroid treatment or non-steroidal anti-inflammatory drugs. Constipation indicative of bowel obstruction should be monitored and effectively managed.

Management of cabozantinib associated non-GI fistula:

Radiation therapy has been identified as a possible predisposing risk factor for non-GI fistula formation in subjects undergoing treatment with drugs that inhibit VEGF pathways. In addition, subjects who have undergone extensive surgery may be at increased risk of developing a fistula of the involved organs. Non GI fistula should be ruled out as appropriate in cases of onset of mucositis after start of therapy. Patients with tumor invading the respiratory tract are also considered a risk for non-GI fistula formation.

Management: Cabozantinib should be discontinued in subjects who have been diagnosed with GI or non GI perforation/fistula that is related to treatment.

5.4.22 Wound Healing and Surgery

Management of cabozantinib-associated wound healing and surgery: Cabozantinib has the potential to cause wound healing complications and wound dehiscence which may even occur long after a wound has been considered healed. Therefore, surgical and traumatic wounds must not only be completely healed prior to starting cabozantinib treatment but must also be monitored for wound dehiscence, wound infection and other signs of impaired wound healing while the subject is being treated with cabozantinib. If dehiscence occurs, cabozantinib treatment should not be restarted until complete healing has taken place.

Treatment with cabozantinib should be stopped at least 28 days prior to scheduled surgery. The decision to resume treatment with cabozantinib after surgery should be based on clinical judgment of adequate wound healing.

The appropriate dose hold interval prior to elective surgery to reduce the risk for wound healing complications has not been determined. When possible, cabozantinib should be stopped at least 28 days prior to elective surgery.

5.4.23 Osteonecrosis of the Jaw

Osteonecrosis has been reported in subjects treated with cabozantinib. Additional risk factors include use of bisphosphonates and denosumab, chemotherapy and anti-angiogenic drugs, use of corticosteroids, local radiotherapy, and dental or orofacial surgery procedures.

Osteonecrosis of the jaw (ONJ) can manifest as jaw pain, osteomyelitis, osteitis, bone erosion, tooth or periodontal infection, toothache, gingival ulceration, or gingival erosion. Persistent pain or slow healing of the mouth or jaw after dental surgery may also be manifestations of osteonecrosis.

Advise subjects regarding oral hygiene practice and to quickly report symptoms to investigator. Caution should be used in subjects receiving bisphosphonates.

Invasive dental procedures should be avoided. In cases where dental procedures are unavoidable, treatment with cabozantinib should be interrupted for at least 4 weeks prior to the procedure and resumed after complete wound healing has occurred. Bone healing may often require a protracted time.

5.4.24 QT (QTcF) Prolongation

Management of cabozantinib-associated QT prolongation:

Treatment with cabozantinib has been associated with a mild prolongation of the QTc interval. Other factors which may contribute to QTc prolongation include

- Treatment with other drugs associated with QTc prolongation (see <http://www.qtdrugs.org>).
- Treatment with CyP 3A4 inhibitors (which may increase cabozantinib drug levels)
- Electrolyte changes (hypokalemia, hypocalcemia, hypomagnesemia).
- Medical conditions which can alter electrolyte status e.g., severe or prolonged diarrhea.

Treatment with drugs that cause QTc prolongation as well as CyP 3A4 inhibitors is discouraged on this study, but not prohibited. Subjects having any of these additional risk factors while on cabozantinib should have ECGs performed approximately one week after the onset of these factors.

If at any time on study there is an increase in QTc interval to an absolute value > 500 msec, two additional ECGs should be performed within 30 minutes after the initial ECG with intervals not less than 3 minutes apart. If the average QTcF from the three ECGs is >500 msec, study treatment must be withheld and the following actions should be taken:

- Check electrolytes, especially potassium, magnesium and calcium. Correct abnormalities as clinically indicated.
- If possible, discontinue any QTc-prolonging concomitant medications.
- Repeat ECG triplets hourly until the average QTcF is ≤ 500 msec or otherwise determined by consultation with a cardiologist.

The Sponsor should be notified immediately of any QTc prolongation event.

Subjects with QTc prolongation and symptoms must be monitored closely until the QTc elevation has resolved. Cardiology consultation is recommended for evaluation and subject management. Symptomatic subjects must be treated according to standard clinical practice.

No additional cabozantinib is to be given to the subject until after the event has resolved, the subject has been thoroughly evaluated, and further treatment has been agreed to by the Study Chair.

If any additional study treatment is given (e.g., after correction of electrolyte abnormalities and normalization of QTcF), it will be at a reduced dose as agreed to by the investigator and the Study Chair.

5.4.25 Guidelines for General Toxicities Commonly Associated with Cabozantinib

As a general approach, it is suggested that all AEs be managed with supportive care when possible at the earliest signs of toxicity. Calcium, magnesium, potassium and phosphorus should be kept above the lower limits of the laboratory normal values. Additional information can be found in the Cabozantinib Investigator's Brochure.

Once reduced, the dose of cabozantinib should not be re-escalated.

General Approach to the Management of Other Cabozantinib-Related Non-Hematologic Adverse Events

Dose Modifications of Cabozantinib for Treatment-Related AEs

CTCAE Grade	Recommended Guidelines for Management ^a
Grade 1 AEs	Add supportive care as indicated. Continue cabozantinib treatment at the current dose level if AE is manageable and tolerable.
Grade 2 AEs which are tolerable and are easily managed Grade 2 AEs which are intolerable and cannot be adequately managed	Continue cabozantinib treatment at the current dose level with supportive care. At the discretion of the investigator, cabozantinib should be dose reduced or interrupted. Note: It is recommended that dose holds be as brief as possible.
Grade 3 AEs (except clinically non-relevant laboratory abnormalities)	Cabozantinib should be interrupted unless the toxicity can be easily managed with a dose reduction and optimal medical care. Note: It is recommended that dose holds be as brief as possible.
Grade 4 AEs (except clinically non-relevant laboratory abnormalities)	Subjects should have cabozantinib interrupted immediately. Discontinue cabozantinib unless the following criteria are met: 
• Subject is deriving clear clinical benefit as determined by the investigator• Toxicity can be managed with a dose reduction following recovery to Grade 1 (or baseline) and optimal medical care
NOTE: A table referencing dose delay and modification criteria for specific medical conditions is provided in Section 5.4.3 . Study treatment dose adjustment is only needed if the toxicity was deemed possibly, probably, or definitely related to cabozantinib treatment.	

5.4.26 Management of other Immune related events

ALL OTHER EVENTS	Management/Next Dose for Nivolumab and combination Nivolumab/Ipilimumab
≤ Grade 1	No change in dose
Grade 2	Hold until ≤ Grade 1 OR baseline(exceptions as noted below)
Grade 3	Off protocol therapy (exceptions as noted below)
Grade 4	Off protocol therapy
Recommended management: As clinically indicated	

Any grade 2 drug-related uveitis or eye pain or blurred vision that does not respond to topical therapy and does not improve to Grade 1 severity within the re-treatment period OR requires systemic treatment should go off protocol treatment

Any adverse event, laboratory abnormality, or intercurrent illness which, in the judgment of the investigator, presents a substantial clinical risk to the subject with continued study drug dosing should go off protocol treatment.

Any grade 3 or 4 drug-related laboratory abnormality or electrolyte abnormality, that can be managed independently from underlying organ pathology with electrolyte replacement, hormone replacement, insulin or that does not require treatment does not require discontinuation.

5.5 Supportive Care and Concomitant Treatments

All supportive measures consistent with optimal patient care will be given throughout the study. There is no mandatory supportive care recommended for study therapy, but general guidelines and doses for specific symptoms are outlined above in the dose modification section.

5.5.1 Concomitant Systemic Treatments

Chemotherapy: Participants are not allowed to receive other anticancer treatment such as chemotherapy while on this trial.

Other Medications: See [Appendix VII](#) for a list of prohibited medications and medications which are permissible but should be used with caution with cabozantinib.

5.5.1.1 Cytochrome P450 substrates

Please refer to the Flockhart drug interaction tables for lists of substrates, inducers, and inhibitors of selected CYP450 isozyme pathways (Flockhart 2007)
<http://medicine.iupui.edu/clinpharm/ddis/>

The FDA drug interaction tables are another source of lists of inducers and inhibitors. "Drug Development and Drug Interactions: Table of Substrates, Inhibitors and Inducers"

<https://www.fda.gov/drugs/developmentapprovalprocess/developmentresources/druginteractionslabeling/ucm093664.htm>

Potent CYP3A4 inducers (see [Appendix VII](#)) are not allowed due to interaction with the metabolism of cabozantinib. Dexamethasone can be used with caution but alternate medications should be considered.

Potent CYP3A4 inhibitors should be avoided. Selection of alternate concomitant medications with no or minimal CYP3A4 enzyme inhibition potential is recommended. Consider dose reduction of cabozantinib in the event of drug interaction.

NOTE: Grapefruit / grapefruit juice and Seville oranges are also strong CYP3A4 inhibitors and consumption should be avoided.

Drugs Associated with QTcF Prolongation

Treatment with cabozantinib has been associated with a mild prolongation of the QTcF interval. Caution should be used when treating subjects on cabozantinib with other drugs associated with QTcF prolongation. Additional QTcF monitoring is suggested for subjects who are treated concomitantly with QTcF prolonging drugs.

5.5.1.2 Other Drugs

Concomitant medications that are highly protein bound (e.g., diazepam, furosemide, dicloxacillin, and propranolol) should be used with caution. Because warfarin is a highly protein bound drug with a low therapeutic index, administration of warfarin at therapeutic doses should be avoided in subjects receiving cabozantinib due to the potential for a protein binding displacement interaction.

In vitro data suggest that cabozantinib is unlikely to be a substrate for P-glycoprotein, but it does appear to have the potential to inhibit the P-glycoprotein transport activity. Therefore, cabozantinib may have the potential to increase plasma concentrations of co-administered substrates of P-glycoprotein.

Cabozantinib was also shown to be a substrate of drug transporter MRP2 in an in vitro assay. Administration of MRP2 inhibitors to subjects may result in increases in cabozantinib plasma concentrations.

Additional details regarding potential drug interactions with cabozantinib can be found in the investigator brochure.

5.5.1.3 Bone Resorption Inhibitors

Bisphosphonates or denosumab should not be added while on study. Patients on these agents prior to

registration are allowed to continue but caution is advised due to increased risk of osteonecrosis of the jaw.

5.5.1.4 **Gastric Acid Inhibitors**

Administration of the PPI esomeprazole resulted in no clinically-relevant effect on cabozantinib plasma PK in healthy volunteers (Study XL184-018). Therefore, concomitant use of gastric pH modifying agents (ie, PPIs, H2 receptor antagonists, and antacids) is not contraindicated in subjects administered cabozantinib. Cimetidine should be avoided due to potential CYP interactions.

5.5.1.5 **Anticoagulants**

Anticoagulation with LMWH and unfractionated heparin is permitted. Low-dose aspirin use is permitted (100mg daily or lower)

No anticoagulation with warfarin or other coumarin-related agents, direct thrombin or direct FXa inhibitors, fondaparinux, antiplatelet agents such as clopidogrel, or aspirin above low dose levels.

5.5.2 **Radiation Therapy**

Radiotherapy for symptomatic management of non-target areas is allowed for up to 10 total fractions of treatment while on trial. Cabozantinib should be held for at least 7 days prior to radiation starting, preferably up to 28 days if feasible. Cabozantinib should continue to be held on days of radiotherapy and for 14 days (2 weeks) after if the radiation is to bone, and for 28 days (4 weeks) for other sites of radiation. Immunotherapy may be continued except on days of radiation.

5.5.3 **Invasive Procedures**

Minor procedures (not involving general anesthesia) are allowed on the study but are discouraged. These include chest tube placement and invasive dental procedures. For patients receiving cabozantinib, it is recommended that patients discontinue treatment 28 days prior and resume treatment after complete wound healing has occurred.

Patients undergoing major surgical procedures may only resume treatment with the approval of the Study Chair.

5.6 **Patient Reported Outcome Measures: Tobacco Use Assessment**

Assessments will be captured directly from the participants using the EASEE-PRO portal. When patients consent to participate, they will be asked to provide a contact email address and that address along with their registration information will be sent directly from the parent trial's registration system to EASEE-PRO, and the patient will be automatically registered into EASEE-PRO for participation. To activate their account for self-directed web entry of surveys, the system will send an activation message to the contact email address that will explain how to activate their account for self-directed web entry of surveys. After their account is

activated, the patient will be able to complete questionnaires using a secure browser interface from any web enabled computer, tablet, or mobile device.

The Core and Extension C-TUQ items will be assessed, together with patient-reported physical and psychological symptoms (See Table 2). Specifically, these items will be administered using the EA SEE-PRO system described in the companion EA NCORP application. The advantage of our virtual electronic data capture system is that our proposed assessments will not be limited to, or dependent upon, patient trial visits. Confidential and potentially stigmatizing information can be provided without requiring direct contact with the care team.

The selected Core and Extension C-TUQ items (from categories of Basic Tobacco Use Information, Tobacco Use in Relation to Cancer Diagnosis and Treatment, Smoking Cessation/Cessation Products/Assistance Methods, Use of Other Products, and Second-Hand Smoke Exposure) will be assessed. The 4-item Short Form PROMIS® for anxiety and depression, the Lung Cancer Stigma Scale, and six symptom items (general pain, fatigue, nausea, cough, sleep difficulties, shortness of breath) from FACIT (Functional Assessment of Chronic Illness Therapy) together with modifications of these same six questions to address the degree of bother associated with each symptom will be administered as well. Additionally, we will ask participants' perceptions of how smoking improves or worsens each of the six symptom experience. All these items will be compiled into Survey of Tobacco Use (STU). Detailed information on various measures is outlined in Appendix VI.

Contents and Corresponding Questions in Survey of Tobacco Use (STU)

Dimension	Source of Measures	Baseline STU	Follow-up STU
Basic Tobacco Use Information	C-TUQ	Q1 – Q5	Q1 – Q2
Tobacco Use in Relation to Cancer Diagnosis and Treatment	C-TUQ	Q6 – Q7	Q3
Smoking Cessation, Cessation Products, and Assistance Methods	C-TUQ	Q8 – Q13	Q4 – Q9
Use of Other Products	C-TUQ	Q14	Q10
Second-Hand Smoke Exposure	C-TUQ	Q15 – Q16	Q11 – Q12
Psychological Symptoms	PROMIS Lung Cancer Stigma Scale	Q17 – Q18	Q13 – Q14
Physical Symptoms	FACIT	Q19	Q15
Sociodemographics		Q20 – 21	

NOTE: In order to minimize ambiguity and assure that patients are oriented to answer appropriately, the specific phrasing of items may vary depending specific cancer type and treatment.

Rev. Add2 i. Assessment Schedule

Survey of Tobacco Use will be administered at the following time points:

1. at baseline (trial enrollment)
2. at 3 month follow-up from study registration
3. at 6 month follow-up from study registration

5.7 Duration of Therapy

Patients will receive protocol therapy unless:

- Patient declines further treatment to withdrawal of consent (Note that patients may decline further treatment without withdrawing consent for follow-up. The different levels of consent withdrawal should be documented in iMedidata/Rave)
- Disease progression by RECIST 1.1 criteria or clinically determined progression.

NOTE: Patients with disease progression by RECIST 1.1 may be continued on treatment as long as they are believed to still have potential clinical benefit from the study therapy and are otherwise medically stable. Generally this is most appropriate for patients with mild asymptomatic radiographic progression.

- Non-protocol anticancer therapies are administered (as outlined in Section [5.5](#), above)
- All study drugs have been held for more than 56 days, unless study chair approves resuming therapy after this point.
- Extraordinary Medical Circumstances: If at any time the constraints of this protocol are detrimental to the patient's health, protocol treatment should be discontinued. In this event submit forms according to the instructions in the EA5152 Forms Packet.

5.8 Duration of Follow-up

For this protocol, all patients, including those who discontinue protocol therapy early, will be followed for radiographic response until progression, even if non-protocol therapy is initiated, and for survival for 5 years following treatment discontinuation. All patients must also be followed through completion of all protocol therapy.

6. Measurement of Effect

6.1 Antitumor Effect – Solid Tumors

For the purposes of this study, patients should be re-evaluated for response approximately every 8 weeks.

Response and progression will be evaluated in this study using the international criteria proposed by the revised Response Evaluation Criteria in Solid Tumors (RECIST) guideline (version 1.1) [Eur J Ca 45:228-247, 2009] with measurements performed at the imaging sites. Changes in the largest diameter (unidimensional measurement) of the tumor lesions and the shortest diameter in the case of malignant lymph nodes are used in RECIST.

The following general principles must be followed:

1. To assess objective response, it is necessary to estimate the overall tumor burden at baseline to which subsequent measurements will be compared. All baseline evaluations should be performed as closely as possible to the beginning of treatment and never more than four weeks before registration.
2. Measurable disease is defined by the presence of at least one measurable lesion.
3. All measurements should be recorded in metric notation by use of a ruler or calipers.
4. The same method of assessment and the same technique must be used to characterize each identified lesion at baseline and during follow-up.

6.1.1 Definitions

Evaluable for Objective Response

Only those patients who have measurable disease present at baseline, have received at least one cycle of therapy, and have had their disease re-evaluated will be considered evaluable for response. These patients will have their response classified according to the definitions stated below.

NOTE: Patients who exhibit objective disease progression prior to the end of cycle 1 will also be considered evaluable.

Evaluable Non-Target Disease Response

Patients who have lesions present at baseline that are evaluable but do not meet the definitions of measurable disease, have received at least one cycle of therapy, and have had their disease re-evaluated will be considered evaluable for non-target lesion assessment. The response assessment is based on the presence, absence, or unequivocal progression of the lesions. It is sometimes permissible to not re-image all non-target lesions at every timepoint, for example, if there are non-clinically significant bone lesions outside of the normal restaging area included in a CT of the chest, abdomen, and pelvis.

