2.2 Secondary Endpoints

- 2.2.1 To estimate the overall survival for each arm of the trial
- 2.2.2 To estimate the best overall response rate for each arm of the trial
- 2.2.3 To estimate the progression free survival of the targeted therapy arm of the trial
- 2.2.4 To describe the toxicity profile of monotherapy with nivolumab, and the combination of nivolumab and cabozantinib, and the combination of nivolumab and cabozantinib and ipilimumab, in this patient population with non-squamous NSCLC.

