NOTE: Prior adjuvant chemotherapy for early stage disease does not count as one line of therapy if 12 months or greater elapsed between completion of adjuvant therapy and initiation of first-line systemic therapy. If less than 12 months elapsed, adjuvant chemotherapy counts as one line of therapy.

Exception for targeted therapy sub-study (Arm T): At least one line of prior chemotherapy or targeted therapy is required, but there is no limit on number of prior treatments.

- 3.2.7 Patients must have measurable disease as defined by RECIST v1.1 criteria in Section 6. Baseline measurements and evaluation of ALL sites of disease must be obtained within 4 weeks prior to registration
- 3.2.8 No prior anti-MET therapy such as crizotinib or cabozantinib, or PD-1/PD-L1 immune checkpoint inhibitor therapy (such as nivolumab, pembrolizumab, atezolizumab) or CTLA4 inhibitor therapy (such as ipilimumab). No prior allergic reaction to small molecule tyrosine kinase inhibitors or monoclonal antibodies.

Exception for targeted therapy sub-study (Arm T): Prior crizotinib may be allowed depending on the gene alteration (see Section 3.1.1)

Rev. Add1

- 3.2.9 Any prior chemotherapy (based on administration schedule) must have been completed in greater than or equal to the following times prior to registration:

Rev. Add3

- Chemotherapy/ targeted oral therapy administered in a daily or weekly schedule must be completed \geq 1 week prior to registration;
- Any chemotherapy administered in an every 2 week or greater schedule must be completed \geq 2 weeks prior to registration.
- Additionally, patients should be recovered to equal to or less than grade 1 toxicities related to any prior treatment, unless AE(s) are clinically nonsignificant and/or stable on supportive therapy.
- 3.2.10 No prior radiation therapy for bone metastasis within 2 weeks, any other radiation therapy within 4 weeks prior to registration.
- 3.2.11 Patients with no known brain metastasis must have baseline brain imaging within 12 weeks prior to study registration not demonstrating brain metastases.
- OR
- Patients with known brain metastases must have baseline brain imaging within 4 weeks prior to study registration and meet all of the following criteria:
- 3.2.11.1 Have completed treatment to all symptomatic brain metastases (with whole brain radiation or radiosurgery) \geq 4 weeks prior to registration, or have undergone complete neurosurgical resection \geq 3 months prior to registration.

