 11. All efforts must be made to assess tumor from the same type of scan that was performed at baseline. A CT scan with contrast involving known systemic areas of disease is recommended. Imagine studies should be done within 4 weeks prior to registration and every 8 weeks (based on Cycle 1 Day 1) during treatment until PD. The imaging should be done within 7 days prior to cycle 3, 5, 7, 9 etc. but may be performed after the treatment for unusual circumstances such as holidays. If drugs are held, the imaging should still be performed every 8 weeks counting from Cycle 1 Day 1.
 12. Patients must have a brain MRI or head CT with contrast at baseline within 12 weeks prior to registration. Patients with known brain metastases at baseline must have a brain MRI or head CT within 4 weeks prior to registration. Patients with known brain metastases should have repeat imaging at least every 16 weeks (4 cycles). Repeat brain imaging is not required for patients without known brain metastases at baseline.
 13. Tumor tissue specimens are required to be submitted for defined laboratory research studies as outlined in Section 10.
 14. All specimens submitted must be entered and tracked via the online ECOG-ACRIN Sample Tracking System (STS).

15. Ipilimumab administration every 8 weeks (cycle 1, 3, 5, 7, etc.)
16. For Arm T patients, to be assigned a status of complete or partial response, changes in tumor measurements must be confirmed by repeat assessments performed no less than four weeks after the criteria for response are first met. Arm A, B, and C patients do not require confirmation scans for complete or partial response.
17. Tobacco use assessment PROs will be collected using EASEE-PRO.
18. Oral daily dosing

Rev. Add4

8. Drug Formulation and Procurement

This information has been prepared by the ECOG-ACRIN Pharmacy and Nursing Committees.

Availability

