9.3 Statistical Analysis Plan

The primary and some secondary analyses will include all eligible and treated patients. Exceptions to this include: analysis of toxicity data, which will include all patients who received study drug regardless of eligibility, and analyses of response, which will include eligible and treated patients with measurable and evaluable disease.

Time-to-event data, such as PFS and OS, will be estimated using the Kaplan-Meier method, and Cox proportional hazards models will be used to estimate the treatment hazard ratios. The primary comparison of PFS will use a logrank test stratified on the randomization stratification factors with a one-sided type I error rate of 10%. Other comparisons of groups will be made using the logrank test and Cox modeling.

Categorical data, such as response rates (CR+PR) and toxicity, will be compared using Fisher's exact tests with a one-sided type I error rate of 10%; multivariable logistic regression modeling will be used to adjust for the effect of any covariates that are associated with these categorical outcomes. Though none are currently planned, any continuous outcomes will be analyzed using Wilcoxon rank sum test, and multivariable linear regression models may be used to adjust for multiple associations with outcome.

Modeling procedures will implement backward selection; variables significant at the 0.10 level in the univariate setting will be chosen for inclusion in an initial full model, and at each step the least significant variable will be removed from the model. Only those covariates with $p < 0.05$ will remain in any final models, unless there are factors identified by the study team as crucial to model interpretation.

Point estimates of all endpoints will be accompanied by the corresponding two-sided 80% confidence intervals.

In the event that there are missing data, no imputation of the missing data will be conducted. We will assume that data are missing at random and will conduct all analyses as originally planned because we do not anticipate an excess of missing data.

Subset analyses are planned for all stratification factors and all known prognostic factors, such as performance status, age, sites of metastases, gender, etc. Subset analyses of all variables, including correlatives, are considered to be exploratory in nature.

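### The response-rate denominator depends on what happens after treatment starts, so the reported ORR is not the rate among treated patients

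*Combined protocol and SAP*

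**What the plan says.** Section 9.3 uses all eligible and treated patients for the primary and some secondary analyses. It then makes an exception for "analyses of response, which will include eligible and treated patients with measurable and evaluable disease". Section 9.2 refers best objective response to Section 6. There, section 6.1.1 restricts evaluability to patients with measurable disease at baseline who "have received at least one cycle of therapy, and have had their disease re-evaluated will be considered evaluable for response". A note adds back patients with objective progression before the end of cycle 1.

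Other relevant provisions:

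- Section 3.2.7 (eligibility): "Patients must have measurable disease as defined by RECIST v1.1 criteria in Section 6".
- Section 7.1, footnote 11 (timing of scans): "The imaging should be done within 7 days prior to cycle 3, 5, 7, 9 etc".
- Section 5.8: "all patients, including those who discontinue protocol therapy early, will be followed for radiographic response until progression". Footnote 3 of section 7.1 asks for scans at least every 3 months in patients who stop before radiographic progression.
- Section 9.3 (missing data): "In the event that there are missing data, no imputation of the missing data will be conducted".
- Section 9.3 (comparison): response rates are compared with Fisher's "exact tests with a one-sided type I error rate of 10" percent.
- Section 2.2.2 (objective): "To estimate the best overall response rate for each arm of the trial". Section 9.4 says Arm T will be described by response rate and PFS.

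**The concern.** Because every eligible patient already has measurable disease, the evaluability rule removes patients only through events after treatment starts. Two groups are lost.

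1. **Never re-evaluated.** The first scheduled re-scan falls in the week before cycle 3. Someone who dies, deteriorates or withdraws before then without an unscheduled scan has no re-evaluation. That person cannot have a documented response, so leaving them out can only raise ORR.
2. **Less than one cycle, without objective progression in cycle 1.** These patients may be scanned later under section 5.8 and footnote 3 of section 7.1, and could respond before the section 6.1.4.4 cut-off (progression or non-protocol therapy). They are still excluded, which can bias ORR in either direction. The documents do not say when a 28-day cycle counts as received.

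The best-response tables in section 6.1.4.4 have no row for a patient without an assessment. Nothing counts such patients as non-responders, asks for an all-treated ORR, or requires non-evaluable counts by arm.

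At stake are the per-arm ORR estimates, the description of Arm T (which has no randomized comparator) and the between-arm Fisher comparison.

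**Working it through.** **Inputs from the documents.** 43 eligible and treated patients per randomized arm (9.4); one-sided 10% Fisher test and 80% confidence intervals (9.3); first re-scan within 7 days before day 57, so from day 57 − 7 = day 50 (7.1); Arm T maximum 90% exact interval width of 35% with 25 enrolled and 56% with 10 (9.4). **Assumed:** the fraction lost d, the number of responders and the true ORR. None is in the documents.

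**The plan's own response figure.** The maximum Clopper-Pearson 90% width is 35.3% at n = 25 and 55.5% at n = 10, matching section 9.4. Those widths are stated for patients enrolled. If 5 of 25 were non-evaluable, the width at n = 20 would be 39.6%.

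**Effect on the estimate.** Let p be ORR among all eligible and treated patients, d the fraction excluded and q the response rate among those excluded:

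ORR(evaluable) = (p − d·q)/(1 − d).

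This exceeds p only if q < p. For the never re-evaluated, q = 0 and the ratio to p is 1/(1 − d):

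| d (assumed) | 1/(1 − d) |
|---|---|
| 5% | 1.05 |
| 10% | 1.11 |
| 15% | 1.18 |
| 20% | 1.25 |

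Illustration with 13 responders among 43: 13/43 = 30.2%, 80% exact CI 21.0% to 40.9%.

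| Excluded | Responders among them | Reported ORR |
|---|---|---|
| 2 | 0 | 13/41 = 31.7% |
| 4 | 0 | 13/39 = 33.3% |
| 8 | 0 | 13/35 = 37.1% |
| 4 | 1 | 12/39 = 30.8% |
| 4 | 2 | 11/39 = 28.2% |

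The last row shows the reversal that the less-than-one-cycle group can cause.

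**Effect on the Fisher test.** Exact enumeration with two arms of 43, equal true ORR p over all 43, and every excluded patient a non-responder. With k patients excluded, responders are binomial on 43 − k patients with probability 43p/(43 − k). The table gives the chance that the one-sided 10% test favours the arm that loses more.

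| True ORR | Loss (arm 1 vs arm 2) | Evaluable only | All treated |
|---|---|---|---|
| 30% | 2 vs 2 | 6.5% | 6.2% |
| 30% | 2 vs 4 | 9.4% | 6.1% |
| 30% | 2 vs 8 | 14.3% | 5.8% |
| 20% | 2 vs 8 | 11.0% | 5.8% |
| 40% | 2 vs 8 | 19.6% | 6.6% |

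At ORR 30% with 2 versus 8, the test favours the arm that loses fewer 2.2% of the time, against 5.9% on all treated.

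**The case against.** The strongest reply concerns size. The documents give no loss rate and no imbalance, and 2 versus 8 is an extreme choice. At 2 versus 4 and ORR 30% the test stays under its nominal 10%, and with equal loss it stays conservative. Each shifted estimate with no responders excluded (31.7%, 33.3%, 37.1%) lies inside the all-treated 80% interval. Losses should also be limited: entry requires ECOG 0–1 and life expectancy above 3 months (3.2.12, 3.2.13), scans keep to the 8-week calendar when drugs are held, imaging continues after early discontinuation, and objective progression in cycle 1 is retained. If the day-1 infusion counts as receiving a cycle, the second group is nearly empty. The restriction is disclosed, response is secondary, and early deaths still count in PFS and OS.

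These points stand as limits on magnitude. They do not restore the missing patients: further scanning shrinks the never-scanned group but leaves whoever remains outside the denominator. An effect smaller than the sampling error is still systematic.

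Section 9.3 speaks of evaluable disease, not of patients evaluable for response, so a looser baseline reading is possible. But section 9.2 points to Section 6, where 6.1.1 is explicit. If the looser reading was meant, the plan still has to say how unassessed patients are counted.

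A lighter remedy, reporting non-evaluable counts plus an all-treated sensitivity analysis, would disclose the problem but leave the selected rate as the main result.

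**Conclusion.** The concern holds. Followed as written, sections 6.1.1 and 9.3 give an ORR conditional on post-baseline events, not the rate among eligible and treated patients. For patients never re-evaluated the bias is upward, with 1/(1 − d) as the upper limit when everyone excluded is in that group. For patients with less than one cycle the direction is open. The Fisher comparison is materially distorted only if loss differs clearly between arms, and the documents do not establish whether it will or which arm would benefit. All sizes rest on assumed losses and response rates. The primary PFS analysis, power and sample size are untouched. This is a change that should be made, not one that threatens the trial's main conclusion.

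**What to change.** - **Sections 9.3 and 6.1.1:** make the main ORR analysis all eligible and treated patients with baseline measurable disease, including Arm T. Use any post-baseline assessment up to the section 6.1.4.4 cut-off, whatever number of cycles was received. Count patients with no post-baseline assessment as non-responders.
- **Section 6.1.4.4:** add a not-evaluable row to both tables.
- **Reporting:** keep the evaluable-only ORR as supportive, and give the number of non-evaluable patients and the reasons, by arm.
- **Section 9.4:** state that the Arm T interval widths apply to the number of patients in the ORR denominator.

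The cost is wording in four sections, with no new patients or data. The reported ORR will usually be slightly lower.
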